## 9. PLANNED STATISTICAL ANALYSES:

The number of each visit (baseline, operative, immediate post-operative follow-up, first follow-up visit, 1 year, 2 years, 3 years) completed will be described as well as the distribution of the latest follow up visit completed. The number and repartition by visit of self-questionnaires will be provided.

### 9.1 Descriptive Analysis (patients, procedure, study exit):

The first tables will describe the patients before the procedure:

#### A. DESCRIPTION BEFORE INTERVENTION

##### *a. Demographic information, urogynecological and medical history*

- General (age, BMI)
- Diagnostic (SUI, MUI)
- Cause of stress component (HU, ISD)
- Previous incontinence treatments
- Previous surgical incontinence treatments
- Lifestyle (activity, smoker)
- Coexisting diseases
- Obstetrical/gynecological history
- Relevant not obstetrical/gynecological surgery or medical history
- History and general symptoms assessment during baseline
- Number of pads used

##### *b. Physical examination / interview patient*

- Result of cough stress test
- Cervico-urethral mobility
  - o Marshall/Bonney Test (sub cervical support maneuver) positive
  - o Ulmsten Test (sub urethral support maneuver)
  - o Q Tip/cotton swab Test:
- Presence of Pelvic Organ Prolapse: localization, grade

*c. Investigations*

- Pad Weight testing
- Post void residual volume (PVR)
- Maximum flow rate (Q max.)

*d. Urodynamic testing*

- Cystometry
- Urethral pressure measurement

*e. Results of patient questionnaires before intervention*

- Demographic questionnaire
- ICIQ- UI SF
- PISQ-12
- I-QOL: total and subscores

**B. PROCEDURE DESCRIPTION**

- Pre-operative and intraoperative antibiotics
- Anesthesia
- Duration
- Blood loss
- Concomitant pelvic surgery
- Technical observations during procedure

**C. DESCRIPTION IMMEDIATE POSTOPERATIVE FOLLOW-UP**

- Post-operative antibiotic
- Normal urination
- Bladder drainage
- Local pain
- Postoperative stay/duration
- Post void residual volume (PVR)
- Maximum flow rate (Q max.)

## D. STUDY EXIT /WITHDRAWAL

- Completion of the study as planned
- Primary reason in case of discontinuation.

### 9.2 Effectiveness Analysis:

#### I. Primary endpoint **at one year:**

- PGI as a little, much better and very better improved and absence of neither severe or serious related Adverse Event classification (as protocol).
- PGI as much better and very better improved, and absence of neither serious or severe or  $\geq$  Grade 3 Clavien-Dindo related Adverse Event (as SC recommendations)

#### II. Secondary endpoints:

- PGI as a little, much better and very better improved and absence of any severe neither serious related Adverse Event at first follow-up visit, 2 years and 3 years after implantation (as protocol).
- PGI as much better and very better improved and absence of neither severe or serious or  $\geq$  Grade 3 Clavien-Dindo classification related Adverse Event at first follow-up visit, 2 years and 3 years after implantation (as SC).
- PGI as much better and very better improved and absence of serious related Adverse Event at first follow-up visit, 1 year, 2 years and 3 years after implantation (as SC).
- PGI as much better and very better improved and absence of  $\geq$  Grade 3 Clavien-Dindo classification related Adverse Event at first follow-up visit, 1 year, 2 years and 3 years after implantation (as SC).
- PGI as a little, much better and very better improved at first follow-up visit, 1 year, 2 years and 3 years after implantation (as protocol).
- PGI as much better and very better improved at first follow-up visit, 1 year, 2 years and 3 years after implantation (as SC).
- Satisfaction at first postoperative visit, 1 year, 2 years and 3 years after implantation.
- Recommendation to a friend at first follow-up visit at 1 year, 2 years and 3 years after implantation.

Evolution over time of continuous outcomes (post-void residual volume, maximum flow rate, pad weight test, number of pads/day, total I-QOL score and subscores, total PISQ-12 score, total ICIQ SF score) or binary variables (cough stress test) will be presented.

The result of these outcomes will be presented for baseline, first operative visit, 1 year, 2 years and 3 years after implantation. Differences with the baseline will be presented and particularly for the questionnaires, where absolute and relative differences of the different scores will be calculated. Evolution will be graphically presented and a smoothing scatter plot of the different parameters over time by using a non-parametric technique (LOESS).

For the self-questionnaires (IQOL, PISQ-12, ICIQ), the cough stress test and number of pads/day: 5 measures are theoretically available by patient (baseline, first follow-up visit, 1 year, 2 years and 3 years), whereas only 3 measures are available by patient for post-void residual volume and peak urine flow rate...

Effect of time will also be tested by a mixed linear model (SAS Proc Mixed) or GEE model (SAS proc genmod). If needed, an extension of mixed model or GEE model such as piecewise linear models will be used to model a potential slope discontinuation over time.

If too many missing data, the alternative is to compare value at 3 years with value at baseline by a Wilcoxon's signed-rank test (continuous variables) or Mc Nemar's test (binary variables).

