surgeons. The data will be captured in an electronic data capture system (EDC).

The Data Collection Schedule below provides an outline of the desired types of clinical and subject data expected to be collected at each visit.

None of these exams are mandatory. If they are performed results will -be collected in the EDC.

	Baseline	Operative period	First Immediate postoperative visit (2 Months \pm 1 Mo) ¹	12 Months visit (1 year \pm 2 Mo) ¹	Yearly follow-up (until 3 years)
Informed consent obtained	X				
Demographic information, urogynecologic history	X				
Body Mass Index	X			X	X
Urodynamics/Uroflowmetry (history)	X				
Urethral mobility & Prolapse anatomy	X				
Physician –rated assessments					
Stress urinary & overactive bladder symptoms	X		X	X	X
Cough stress test	X		X	X	X ²
Post void residual urine volume	X	X	X	X ³	
Adverse Event assessment		X	X	X	X
Patient-reported outcomes					
Number of pad/day	X		X	X	X
ICIQ-UI SF & I-QOL & PISQ12	X		X	X	X
PGI-I			X	X	X
Subject satisfaction			X	X	X

1 windows are given for information

2 not requested if data are obtained only by mailed questionnaires

3 not requested if the previous value is normal

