### 4.1 Primary endpoint:

As defined in protocol:

Treatment success defined by PGI as a little, much better and very better improved and absence of serious or severe related Adverse Event one year after implantation.

Table 1: Definition of treatment success

Patient Global Improvement (PGI-I)	Safety	
	No severe or serious related adverse event reported	At least one severe or serious adverse event reported
Very much better	success	failure
Much better	success	failure
Little better	Success	failure
No change	failure	failure
Little worse	failure	failure
Much worse	failure	failure
Very much worse	failure	failure

As recommended and defined by Scientific Committee /SC:

- Treatment success defined by PGI as much better and very better improved and absence of any serious neither severe nor  $\geq$  grade 3 of Clavien-Dindo classification related Adverse Event one year after implantation.

4.2 Secondary endpoints:

As defined in protocol:

- ✓ Treatment success defined by PGI as a little, much better and very better improved and absence of serious or severe related Adverse Event at first follow-up visit, 2 years and 3 years after implantation.
- ✓ PGI as a little, much better and very better improved at first follow-up visit, 1 year, 2 years and 3 years after implantation.

As recommended and defined by Scientific Committee /SC:

- ✓ Treatment success defined by PGI as much better and very better improved and absence of any serious neither severe nor  $\geq$  grade 3 of Clavien-Dindo classification related Adverse Event at first follow-up visit, 2 years and 3 years after implantation.

- ✓ PGI as much better and very better improved at first follow-up visit, 1 year, 2 years and 3 years after implantation.
- ✓ Treatment success defined by PGI as much better and very better improved, and absence of serious related Adverse Event at first follow-up visit, 1 year, 2 years and 3 years after implantation.
- ✓ Treatment success defined by PGI as much better and very better improved, and absence of  $\geq$  Grade 3 Clavien-Dindo classification related Adverse Event at first follow-up visit, 1 year, 2 years and 3 years after implantation.
- ✓ PGI as much better and very better improved at first follow-up visit, 1 year, 2 years and 3 years after implantation.

Objective exams at baseline, first follow-up visit, one year, two years, three years after implantation:

- ✓ cough stress test,
- ✓ number of pads/day,
- ✓ post-void residual volume,
- ✓ maximum urinary flow rate,

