## **7. HANDLING OF MISSING VALUES:**

Missing data will remain missing in all endpoint derivations except for I-QOL and PISQ-12 questionnaires for whom specific guidelines will be applied. All summary tables will be based on data without imputation of missing values.

For multivariate logistic regression (study of factors associated to success of treatment), if missing values concern most of the covariates, multiple imputation may be needed. In that case, Proc Mi & Proc Mianalyse (SAS 9.4) will be used.

Multiple imputation inference involves three distinct phases:

1. The missing data are filled in  $m$  times to generate  $m$  complete data sets. (Proc Mi)
2. The  $m$  complete data sets are analyzed using standard statistical analyses. (Proc Mi)
3. The results from the  $m$  complete data sets are combined to produce inferential results (Proc Mianalyse).

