### For effectiveness analyses:

In order to present a smoothing scatter plot of these parameters' evolution over time, a non-parametric technique called LOESS will be used: LOESS is a type of local polynomial regression and is a generalization of moving average and polynomial regression; LOESS fits a localized regression function to data with a chosen neighborhood of points. At each point of the dataset, a low degree polynomial (linear or quadratic) is fitted to a subset of the data, with explanatory variables values near the point, whose response is being estimated: the polynomial is fitted using weighted least squares, giving more weight to points near the point whose response is being estimated and less weight to points further away. The value of the regression function is then obtained by evaluating the local polynomial using the

[figure not shown]
explanatory variables value which are in the local neighbourhood for that data point. The LOESS fit is complete after regression function values have been computed for each of the data points.

Furthermore, these repeated data are inherently unbalanced because patients did not come to all planned visits (missing data) and because the time between 2 consecutive visits is not always the same.

Consequently, specific longitudinal models must be used to take into account these unbalanced data. Mixed models containing fixed effects and random effects (intercept and/or slope) must be used and specific covariance structure to model within subject variation (R matrix) must be chosen.

If the smoothing scatter plot suggests trends with slope discontinuation over time, a mixed piecewise linear model including knots will be used.

The following pattern illustrates such piecewise linear models.

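### SAP 9.2 replaces the all-visit model by complete-pair baseline-to-3-year tests when an undefined amount of data is missing, and the SAP takes no account of conditional collection of residual volume and cough test

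*SAP*

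**What the plan says.** **Planned model.** SAP section 8 (effectiveness analyses) notes that women miss visits and that visit spacing varies, and concludes: "Consequently, specific longitudinal models must be used to take into account these unbalanced data". SAP 9.2 II follows this: "Effect of time will also be tested by a mixed linear model (SAS Proc Mixed) or GEE model (SAS proc genmod").

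**Fallback.** The next paragraph of SAP 9.2 II reads: "If too many missing data, the alternative is to compare value at 3 years with value at baseline by a" Wilcoxon signed-rank test, or McNemar's test for binary variables. How much missing data triggers the switch is not stated.

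**Missing values.** SAP section 7 says: "All summary tables will be based on data without imputation of missing values". Multiple imputation is allowed only for the regression on success factors. SAP section 8 computes percentages on non-missing data.

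**PVR and flow rate.** SAP 4.2 lists them under "Objective exams at baseline, first follow-up visit, one year, two years, three years after implantation". SAP 9.2 II also promises results at all five visits, but then says that "only 3 measures are available by patient for post-void residual volume and peak urine flow rate". The protocol's Data Collection Schedule has no PVR in the yearly column and lists uroflowmetry at baseline only, as history.

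**Conditional collection.** Schedule footnote 3 makes the 12-month PVR "not requested if the previous value is normal". Footnote 2 makes the yearly cough test "not requested if data are obtained only by mailed questionnaires". The schedule adds that no exam is mandatory and that results of exams performed are collected. SAP 2.1 leaves the choice of site visit or post in years 2 and 3 to the surgeon. SAP 9.2 II counts five cough tests per woman as theoretically available. The SAP mentions neither footnote.

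**The concern.** The fallback removes the right method when it is most needed. A likelihood-based model over all visits uses the first-visit, 1-year and 2-year scores, which carry information about who later drops out. A paired test of baseline against 3 years ignores them and describes only women with both values. With no threshold, the choice can also be made after the data are seen.

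For PVR and flow rate the fallback cannot run as scheduled. For the cough test, McNemar's test at 3 years would be confined to women who were examined on site.

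The footnotes raise a separate problem for the visit-by-visit tables. Twelve-month PVR is requested selectively from women whose previous value was not normal, so a raw comparison with baseline can show a worsening that did not occur. Late cough-test results depend on who attends in person. SAP section 5 gives a special code only to 3-year data not yet due at extraction, so a value never requested will look like any other missing value.

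At stake is the secondary objective of effectiveness over 3 years.

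**Working it through.** The plan has no figure of its own to reproduce here. It gives no 3-year missingness rate; the only stated attrition is 20%, in the sample-size section (SAP 2.2). Everything below except the enrolment of about 600 is an assumption used for illustration.

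**1. Complete pairs on the ICIQ score.**
- Assumed means: 14 at baseline, 4.5 at 1 year, 6 at 3 years, a true change of about -8 (-7.99 in the simulated data).
- Assumed SDs: 4 at baseline, 5 afterwards. Correlations: 0.3 with baseline, 0.6 between 1 and 3 years.
- Assumed missingness: 41% at 3 years, leaving about 353 of 600. The odds of dropout are multiplied by a fixed ratio per SD of the 1-year score.
- Bias = (0.6 × 5 − 0.3 × 4) × m = 1.8 × m, where m is the mean standardised 1-year score among women retained.

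| Odds ratio per SD | m | Bias | Complete-pair change | Bias / true change |
|---|---|---|---|---|
| 1.0 | 0 | 0 | -7.99 | 0% |
| 1.5 | -0.16 | -0.29 | -8.28 | 0.29 / 7.99 = 3.6% |
| 2.0 | -0.26 | -0.47 | -8.46 | 0.47 / 7.99 = 5.9% |

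Using the 1-year score recovers -8.00 at odds ratio 2.0. This is by construction, because dropout was generated from that score.

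Precision: SD of change = √(16 + 25 − 2 × 0.3 × 4 × 5) = √29 = 5.39. Standard error = 5.39/√353 = 0.287. The 95% half-width = 1.96 × 0.287 = 0.56, so a bias of 0.47 is nearly as large. The test itself is not in doubt: 7.99/0.287 is about 28 standard errors.

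A second simulation used five visits, a true change of 1.50 SD and dropout depending on the previous score. Complete pairs gave 1.54 SD with 71% retained (3% too high) and at most 1.71 SD with 34% retained (14%). The all-visit estimate stayed at 1.49 to 1.51. With dropout unrelated to outcome, both methods gave 1.50.

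**2. Twelve-month PVR under footnote 3.** Let a be the share abnormal at the first visit; q1 = 0.40 and q0 = 0.03 the chances of an abnormal 12-month value after an abnormal or normal one; and m1 = 0.90 and m0 the shares re-measured.

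Observed abnormal share = (a·m1·q1 + (1−a)·m0·q0) / (a·m1 + (1−a)·m0).

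With a = 0.10 the true share is 0.10 × 0.40 + 0.90 × 0.03 = 6.7%. Observed:
- m0 = 0: 0.036/0.09 = 40%
- m0 = 0.2: (0.036 + 0.0054)/(0.09 + 0.18) = 15%
- m0 = 0.5: (0.036 + 0.0135)/(0.09 + 0.45) = 9%

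On the mL scale (no true change, median 20 mL, log-SD 0.9, correlation 0.4), the observed 12-month median is about 35 mL (normal up to 50 mL) or 44 mL (up to 100 mL) if no previously normal woman is re-measured. It is about 25 or 22 mL if 20% of them are.

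**3. Late cough tests under footnote 2.** With 15% truly positive:
- 60% of positive and 40% of negative women seen on site: 0.09/(0.09 + 0.34) = 21% observed
- 70% and 30%: 0.105/(0.105 + 0.255) = 29%
- 40% and 60%: 0.06/(0.06 + 0.51) = 11%

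The distortion can go either way.

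**4. PVR and flow rate at 3 years.** SAP 4.2 lists five time points and SAP 9.2 II counts three measures; the protocol schedules no yearly PVR and no follow-up flow rate. No assumption is needed: the passages disagree, and the baseline-to-3-year test has no scheduled 3-year value.

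**The case against.** - **The SAP knows these data are incomplete.** A reader might infer that it treats PVR and cough test as routinely measured. It does not: SAP 3.3 lists PVR and flow rate as subject to availability, SAP 9.2 II calls the five cough tests theoretical, and section 8 reports N and, for discrete variables, missing counts. What stands is that no planned table or test allows for the conditional collection.
- **Not requested is not the same as not done.** A reader might infer that every woman with a 12-month PVR had an earlier abnormal value. The protocol collects any exam performed, so previously normal women may appear. The larger figures in step 2 assume that none do, and the excess shrinks quickly once some are re-measured.
- **The bias is assumed, and the test is safe.** A reader might infer that the 3-year finding of improvement could be overturned. At about 28 standard errors a shift of 0.47 cannot do that; it affects the estimated change. Nor is completely random dropout required: complete pairs are also unbiased when dropout depends on factors unrelated to the change.
- **Removing the fallback does not cure everything.** The visit summaries use observed data in any case, and 1- and 2-year results are presented whether or not the fallback is used. This is correct, and it is why the tables need their own correction.
- **A mixed model is not a full remedy.** This also stands: it cannot remove cough-test selection that depends on current symptoms.

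**Conclusion.** The point holds for secondary endpoints. The fallback contradicts the SAP's own reason for using longitudinal models, has no trigger, discards the intermediate visits, and has no scheduled 3-year data for PVR or flow rate. These conclusions rest on the text alone.

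The size of the bias does not. It is about 3 to 6% of the 3-year change under moderate assumed inputs, larger only with much heavier loss, and nil if dropout is unrelated to outcome. Complete pairs flatter the device only if poor responders drop out more, which the documents do not establish. Raw 12-month PVR would tend to look worse than it is, by an amount that depends on how many previously normal women are re-measured. The cough-test distortion has no known direction.

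A reader might extend this to the main result. The documents do not support that: the 1-year composite uses PGI-I and adverse events, and neither the fallback nor the two footnotes apply to it.

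**What to change.** 1. **SAP 9.2 II, model.** Keep a likelihood-based mixed model over all visits as the main analysis whatever the amount of missing data. If it does not converge, simplify the covariance or random effects. Log-transform PVR if skewed. For the cough test use a logistic mixed model, because unweighted GEE needs stronger missingness assumptions; this is an addition, since the SAP names only a linear mixed model or GEE.
2. **Paired tests.** Retain Wilcoxon and McNemar only as a labelled sensitivity analysis in women with both values.
3. **SAP 4.2 against 9.2 II.** Reconcile them by removing PVR and flow rate at 2 and 3 years from the endpoint list and the five-visit presentation.
4. **Twelve-month PVR.** Report the model-based estimate using earlier PVR values. Split the raw table by whether the previous value was normal or abnormal, state the cut-off (the SAP uses 50, 100 and 150 mL in different places), and count not requested separately from missing.
5. **Cough test, years 2 and 3.** Label the results as women seen on site, compare their 1-year PGI-I and ICIQ with those of mail-only women, and state that the model cannot remove selection on current symptoms.

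The cost is revised SAP wording, slightly more analysis work and a few table columns. No new data are needed.

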### 9.3 Safety endpoints:

A review by a Safety Committee will take place in order to classify the events declared into side effects events, technical observations and post-operative observations. This committee will also adjudicate on the relatedness of events (procedure or device), their seriousness, preferred term and classify them according the Clavien-Dindo classification).

The Safety Data Committee will adjudicate on the events reported by patients in the patient's questionnaires and not confirmed as related by the investigator.

The Clavien-Dindo is widely used throughout surgery for grading events (complications) which occur as a result of surgical procedures, grading complications by the extent of therapy necessary to resolve them.

[figure not shown]
The adjudication by the Safety Committee will be considered as the final decision.

[figure not shown]
Tables will present the following data concerning side effects occurred since implantation: type, severity, intensity, relatedness (device/procedure), Clavien-Dindo classification, Side-Effect

[figure not shown]
(=Preferred Terms when possible), SOC and High Level Term according to MedDRA, sling revisions (and description), treatments given and localization (if pain), according to time of clinically diagnosed (intraoperative vs postoperative and IUGA Time division from T1 to T4).

Incidence rates with 95% confidence interval will be calculated between operative procedure and the last follow-up visit available with an exact method based on the Poisson distribution on 'SOC' and 'High Level' terms (MedDRA classification), except for 'High Level'= pain which will be divided into 2 possible Side-Effects: 'Non urogenital pain' or 'Urogenital pain'.

The distribution of mean of cumulated events over time, taking into account that multiple events per patient may occur, will also be presented globally or stratified by the main 'High Level Term' ('Bladder storage symptoms', 'exposure and extrusion', 'Urinary Tract Infection', 'Voiding symptoms', 'pain' itself divided into 'Non urogenital pain' or 'Urogenital pain').

#### **10. SOFTWARE:**

All statistical analysis and programming will be done using the SAS software version 14.3.
